11.7.2 Secondary Efficacy Endpoints

The secondary endpoints for this study are:

- Mean change in BCVA from baseline in the study eye at the end of 3 months, assessed with the ETDRS chart.
- Mean change in BCVA from baseline in the study eye at the end of 6 and 9 months, assessed with the ETDRS chart.

All efficacy endpoints will be summarized descriptively by treatment and time point. Continuous endpoints will be presented using sample size, mean, SD, minimum, median, and maximum, and categorical will be presented using sample size and percentages. Summarization will be presented for both PPS and FAS. For these summaries, no imputation of missing data will be used.

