11.2.2 Criteria for Equivalence

Equivalence will be determined based on the change from baseline in BCVA at Month 12. An equivalence margin of 4 letters will be used. If the 90%[#] (2-sided) confidence interval for the difference in means in change from baseline at month 12 is wholly within the equivalence margin (-4, 4), then the null hypothesis

$$H_0: \mu_1 - \mu_2 \leq -4 \text{ or } \mu_1 - \mu_2 \geq 4$$

will be rejected in favor of the alternative hypothesis

$$H_A: |\mu_1 - \mu_2| < 4,$$

where μ_1 represents the population mean change from baseline for patients treated with LUBT010, and μ_2 represents the population mean change from baseline for patients treated with Lucentis[®]. (# As generally required by US Food and Drug Administration [FDA])

Similar methodology will be used with 95%^{##} CI for difference. Thus, if 95% (2-sided) confidence interval, lies wholly within the equivalence margin (-4, 4), then the null hypothesis will be rejected. (## As generally required by the European Medicines Agency [EMA].)

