11.7 Efficacy Analysis

11.7.1 Primary Efficacy Endpoint

The primary endpoint is mean change in BCVA from baseline in the study eye at the end of 12 months, assessed with the ETDRS chart.

The primary endpoint will be analyzed using ANCOVA model with fixed-effect treatment, and baseline BCVA as covariate.

Denote the population parameter for the mean change from baseline in BCVA by θ_R for LUBT010 arm, and by θ_L for Lucentis® arm, expressed in letters. The hypothesis to be tested will be

$$H_0: \theta_R - \theta_L \leq -4 \text{ or } 4 \leq \theta_R - \theta_L \text{ versus } H_A: -4 < \theta_R - \theta_L < 4.$$

The hypothesis will be tested using the two-sided 90% confidence interval for the difference as accepted by US FDA. If the 90% confidence interval lies wholly between -4 and 4, then the

null hypothesis will be rejected. The confidence interval will be constructed using a two-sample t-test.

Similar methodology will be used with 95% CI of mean difference for EMA. Thus, if 95% (2-sided) confidence interval, lies wholly within the equivalence margin (-4, 4), then the null hypothesis will be rejected.

Missing data in the primary endpoint will be imputed by multiple imputation approach under the assumption of outcome is Missing At Random (MAR). The MAR assumption will be implemented using ANCOVA model by repeated imputation of missing values in primary endpoint. For this assumption, missing outcomes are modeled using observations from a patient's own treatment arm. Thus, MAR would tend to reflect in the missing data any observed differences between treatment groups and is appropriately conservative for the objective of assessing equivalence. Then, to assess the robustness of MAR assumption in primary analysis, the sensitivity analysis via tipping point approach under the Missing Not At Random (MNAR) assumption will be performed.

Details will be provided in the SAP, which will be finalized and signed prior to database lock and unblinding

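### The protocol plans no LUBT010 minus Lucentis estimate with a confidence interval for BCVA change at Months 3, 6 and 9, only unadjusted observed-case summaries by arm

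*Combined protocol and SAP*

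**What the plan says.** Section 11.7.2 lists two secondary efficacy items: "Mean change in BCVA from baseline in the study eye at the end of 3 months, assessed with the ETDRS chart" and "Mean change in BCVA from baseline in the study eye at the end of 6 and 9 months, assessed with the ETDRS chart". It then gives the analysis:

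- The general rule is "All efficacy endpoints will be summarized descriptively by treatment and time point".
- On content, "Continuous endpoints will be presented using sample size, mean, SD, minimum, median, and maximum".
- On populations, "Summarization will be presented for both PPS and FAS".
- On missing values, "For these summaries, no imputation of missing data will be used".

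No treatment difference, model or interval for these visits appears there, in the synopsis or in Section 8.

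Month 12 is handled differently. Section 11.7.1 says "The primary endpoint will be analyzed using ANCOVA model with fixed-effect treatment, and baseline BCVA as covariate", and adds 90% and 95% intervals, multiple imputation under MAR and a tipping-point analysis. Section 11.2.2 confines the decision to that visit: "Equivalence will be determined based on the change from baseline in BCVA at Month 12". Section 11.2 leaves detailed methodology, and any additional analyses, to a SAP to be finalised before database lock. The supplied text contains no SAP wording on the secondary efficacy endpoints.

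**The concern.** The trial exists to compare two products, so the quantity of interest at any visit is the difference between arms. The secondary endpoints are the same measurement as the primary, in the same patients, at visits where BCVA is already scheduled. Yet the stated method drops three things used at Month 12: the between-arm estimate with its interval, the baseline covariate, and the MAR handling of missing data.

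The last of these matters because an arm mean of observed cases is generally unbiased only if missingness is unrelated to outcome, which is a stronger condition than MAR. Section 11.3 itself names treatment failure, treatment success and adverse events as possible reasons for missing data. The plan is also uneven: Section 11.8.1.7 calls for the incidence of antibodies to be tested between arms at Months 1, 3, 6, 9 and 12, while the named secondary efficacy endpoints receive no between-arm estimate.

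What is at stake is how well the earlier course of response can be read alongside the Month 12 result. Two columns of arm means, with no interval for their difference, leave each reader to judge by eye whether a gap is noise.

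**Working it through.** **1. Comparison of the two specifications**

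| Feature | Month 12 (11.2.2, 11.7.1) | Months 3, 6, 9 (11.7.2) |
|---|---|---|
| Between-arm difference | Yes | Not stated |
| Interval | 90% and 95% | Not stated |
| Baseline BCVA adjustment | Yes | Not stated |
| Missing data | Multiple imputation under MAR, then tipping point | Observed cases |
| Margin | 4 letters | None set |

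**2. The plan's own sample size (Section 11.1)**

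Inputs: SD 14.5, margin 4, two-sided 5%, power 80%, 279 per arm, 7% dropout. A true difference of zero is assumed, since none is stated. For two one-sided tests:

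n per arm = 2 × [SD × (z(1−α) + z(1−β/2)) / margin]²

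- With one-sided α = 0.025 (the 95% interval): 2 × [14.5 × (1.960 + 1.282) / 4]² ≈ 276.1, so 277 per arm. Exact t-based power at 279 per arm is 80.4%.
- With one-sided α = 0.05 (the 90% interval): 226 per arm, which does not match.
- Dropout: 558 / (1 − 0.07) = 600.

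The stated numbers reproduce on the 95% interval. Nothing in this point disputes them.

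**3. Precision available at Months 3, 6 and 9**

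The documents give no SD for these visits, so a range of 10 to 14.5 letters is assumed. Its upper end is the Month 12 planning value. For an unadjusted difference:

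SE = SD × √(2/n); half-width = t × SE, on 2n − 2 = 556 degrees of freedom at n = 279.

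Worked case: 14.5 × √(2/279) = 1.228. Multiplying by about 1.964 gives 2.41 (95%), and by about 1.648 gives 2.02 (90%).

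| Assumed SD | SE | 90% half-width | 95% half-width |
|---|---|---|---|
| 10 | 0.847 | 1.39 | 1.66 |
| 12 | 1.016 | 1.67 | 2.00 |
| 14.5 | 1.228 | 2.02 | 2.41 |

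The table is computed from unrounded SEs. Varying the number observed at SD 14.5 changes little: the 95% half-width is 2.47 letters with 265 per arm and 2.33 with 300. Baseline adjustment would be expected to narrow these figures.

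**4. What the planned summaries allow**

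The per-arm n, mean and SD are enough to compute an unadjusted observed-case difference and its interval. They carry no information on how baseline relates to later BCVA, or on patients with missing values. The baseline-adjusted and MAR-based versions therefore cannot be reconstructed from them.

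**The case against.** **The SAP may supply it.** Section 11.2 describes the analysis as foreseen at planning and sends additional analyses to the SAP. A reader might infer that the trial will produce no between-arm estimate before Month 12; the documents do not support that. What stands is narrower. Section 11.7.2 states a specific method for these endpoints and, unlike Sections 11.7.1 and 11.7.3, does not itself point to the SAP. A general deferral does not alter that method.

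**The sentence is not exclusive.** Read literally, the descriptive rule covers all efficacy endpoints, including the primary, which also has an ANCOVA. That is fair: the rule does not forbid a comparison. But for Months 3, 6 and 9 no other text supplies one.

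**Descriptive secondaries are legitimate.** Section 4.2 gives only safety and immunogenicity as secondary objectives, and equivalence is tied to Month 12. This stands, and it is why only a supportive estimate is asked for, not a test.

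**Precision is not wholly absent.** A reader might infer that the arm means come with no measure of precision. They come with n and SD, so the loss is limited to the adjusted and MAR-based versions.

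**The missing-data effect may be small.** Assumed dropout is 7% by Month 12, and cumulative dropout at earlier visits cannot exceed that. The bias from observed cases is not quantified here and should not be presented as large.

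**Conclusion.** The point holds as a gap in the protocol's stated analysis, of moderate to low weight. For its only secondary efficacy endpoints, a comparative trial plans arm-level, unadjusted, observed-case summaries and no estimate of the difference with an interval. An informative estimate is available from data already scheduled: a 95% half-width of about 1.7 to 2.4 letters before adjustment. That range rests on 279 observed per arm and an assumed SD of 10 to 14.5 letters.

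Three further inferences are not supported:

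- **That the primary result is weakened.** The Month 12 analysis and its error rate do not depend on Section 11.7.2.
- **That these half-widths would show equivalence earlier.** The 4-letter margin is set for Month 12 only. Even if it were borrowed, a half-width below 4 does not place the interval inside ±4: at SD 14.5, 279 per arm and zero true difference, the 95% interval falls inside about 80% of the time.
- **That Month 3 has special status.** It has its own bullet, but no section ranks it above Months 6 and 9.

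**What to change.** In Section 11.7.2, and carried into the SAP before unblinding, add for Months 3, 6 and 9 the estimated LUBT010 minus Lucentis difference in change in BCVA with 90% and 95% confidence intervals. Use the primary ANCOVA (treatment, baseline BCVA) with the same MAR imputation, in the FAS and repeated in the PPS. Label the results supportive and state that no formal equivalence test is made at these visits. The descriptive summaries can stay as they are.

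Using the primary model keeps the earlier estimates on the same footing as Month 12. The cost is protocol and SAP text plus programming. It needs no new data, visits or patients and has no effect on the Month 12 error rate.

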11.7.3 Exploratory Endpoint

The exploratory endpoint for the study is:

- Mean change from baseline in NEI-VFQ-25 Version 2000 (interviewer administered) scores at 3, 6, and 12 months.

The NEI-VFQ-25, Version 2000, will be administered by the interviewer at baseline, 3, 6, and 12 months, and the scores obtained will be summarized using number of patients, mean, SD, minimum, median, and maximum, by treatment group and scheduled visit. No imputation will be performed. Data from exploratory endpoints will be summarized using appropriate descriptive statistics and also listed as applicable. Details will be provided in SAP.

11.8 Safety Analysis

The safety data will be summarized and listed. Detailed statistical methodology will be described in SAP.

11.8.1 Parameters for Assessment of Safety

- AE assessment, ocular and non-ocular
- Ophthalmic examination
- Physical and systemic examination
- Vital signs
- ECGs
- Laboratory parameters: Blood (hematology and biochemistry) and urinalysis

11.8.1.1 Adverse Events

All AEs will be coded by System Organ Class (SOC) and Preferred Term (PT) according to the Medical Dictionary for Regulatory Activities (MedDRA) version 19.1 or higher. Events will be classified as TEAEs if they start on or after the date of the first dose of study medication. The number of AEs and the number and percentage of patients experiencing AEs will be summarized by severity and relationship to the study medication. SAEs and AEs leading to premature study discontinuation will be summarized. The corresponding listings will be provided. Study drug injection sites will be assessed for injection site reactions/ inflammatory reactions at each study visit.

11.8.1.2 Ophthalmic Examination

Ophthalmic examination findings will be summarized using appropriate descriptive statistics and also listed as applicable.

11.8.1.3 Physical & Systemic Examinations and Electrocardiogram Measurements

Changes in the physical and systemic examinations and 12-lead ECG findings from screening to the end of IP will be listed.

11.8.1.4 Laboratory Data

Descriptive statistics will be performed for laboratory parameters at each scheduled visit and for the changes from baseline, by treatment and time point. For continuous outcomes, summaries will include sample size, mean, SD, minimum, median, and maximum. Abnormal values in each treatment arm will be determined and listed using reference ranges provided by the central laboratory. All laboratory results will be listed, including data from the unscheduled visits.

11.8.1.5 Vital Signs

Changes in vital signs (pulse rate, respiratory rate, body temperature, blood pressure) from baseline to vital signs assessment at subsequent visits will be summarized. The corresponding listing will be provided.

11.8.1.6 Prior and Concomitant Medications

Prior and concomitant medications will be coded using the WHO-Drug Dictionary classification and a listing will be prepared. All medications that are ongoing during the study and concomitant medications received after randomization will be summarized.

11.8.1.7 Analysis of Immunogenicity

The immunogenicity data reflect the proportion of patients whose test results will be considered positive for antibodies to ranibizumab in immunoassays. The incidence of immunogenicity to ranibizumab will be tested between treatment arms on Day 1 and at the end of 1, 3, 6, 9, and 12 months.

A similar analysis will be performed for the proportion of patients with positive neutralizing antibodies to ranibizumab.

In this study, if at least one sample tests positive in the validated method during this study, the patient is evaluated as a positive patient.

Details about analysis of immunogenicity will be provided in the SAP.

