- 13 To be performed pre-treatment
- 14 Predose (both eyes) & Post dose (study eye only)
- 15 Measurement method used for a patient to be preferably consistent throughout the study
- 16 Obtained pre-treatment for both eyes and 60 min (\pm 30 min) post injection for study eye only
- 17 Fundus photographs/ soft copy to be retained as source document
- 18 Known history of sensitivity to fluorescein dye to be checked before Fluorescein angiography
- 19 To be done in both eyes at screening and in study eye after every injection within a month unless not considered necessary by PI as decided by clinical examination.
- 20 Blood samples for immunogenicity to be collected, before dosing study drug (predose) at Day 1, Day 31, Day 91, Day 181, Day 271, and at EOS visit (Day 360).
- 21 In case of early discontinuations/ premature termination of the study all EOS investigations should be done on the day of termination as far as possible.

Figure 1: Study Flow Chart

- o D = Day
- o  - Lucentis® or LUBT010 injection to be given intravitreally for 12 months at following monthly visits: D1, D31, D61, D91, D121, D151, D181, D211, D241, D271, D301, and D331 with an allowable visit window period of \pm 2 days.
- o Patients will visit site for a safety visit after the first dose on any day during Day 2 to 9. A post injection visit/ telephonic safety assessment after every injection will be done as deemed necessary by Investigator. Day 331 will be the End of Treatment (EOT) visit and Day 360 will be the End of Study (EOS)visit.
- o Efficacy & Safety assessments will be done at monthly visits. Immunogenicity testing will be done at Day 1 and at the end of 1 month (D31), 3 months (D91), 6 months (D181), 9 months (D271), and 12 months (D360).

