This study has mean change in Best Corrected Visual Acuity (BCVA) from baseline as the primary endpoint. This is a globally accepted primary end point. The methodology used to measure visual acuity is by using Early Treatment Diabetic Retinopathy Study (ETDRS) chart which has been endorsed by the Food and Drug Administration (FDA).¹³ Assessment of immunogenicity is of critical importance to characterize potential differences between the biosimilar candidate and the reference medicinal product in terms of the incidence and severity of human immune responses and is considered a key component of a biosimilar’s clinical development program. Since both pre-treatment and post treatment incidences of antibodies have been reported with Lucentis®, comparative immunogenicity assessment has also been included in this trial.

This study includes monthly injections of ranibizumab (LUBT010 or Lucentis®) for a treatment duration of 12 months. The US prescribing information for Lucentis® recommends monthly injections for optimal visual acuity outcomes. Studies have also suggested higher efficacy with monthly regimen as compared to PRN regimen with statistically significant difference of 2.4 letters found in favor of monthly dosing compared with PRN treatment.⁹ Neovascular AMD, being a chronic progressive disease, patients are required to receive therapy for long duration. In addition, the landmark trials for ranibizumab (ANCHOR¹⁴ MARINA¹⁵ and HARBOR¹⁶) have satisfactorily evaluated the primary endpoints with 12 monthly injections. As per the MARINA trial results, more than 90% of patients in each treatment group remained in the study at 12 months, thus meeting the endpoints satisfactorily. Therefore, a study duration of 12 months with monthly injection intervals is considered appropriate for assessment of efficacy, safety, and immunogenicity in this study.

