5.2.3 Immunogenicity

Proportion of patients with anti-drug antibodies at the end of 1, 3, 6, 9, and 12 months.

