6.3.1.2 Treatment Period (12 months)

6.3.1.2.1 Day 1 (Randomization and Ranibizumab First Dose Administration)

Randomization should be performed within maximum of 28 days of screening.

Day 1 (Predose)

- Vital signs assessment
- Urine pregnancy test (in females of childbearing potential [females who are not surgically sterile or menopausal])
- Perform physical and systemic examination
- Confirmation of eligibility based on screening results and investigations done on Day 1

- Ophthalmic Examinations: Unless otherwise stated these will be done for both the eyes
 - Refraction assessment
 - BCVA using ETDRS*
 - Ophthalmoscopic examination
 - IOP measurement
 - Slit lamp examination
- Interviewer administered NEI-VFQ-25 (baseline)
- Immunogenicity (anti-drug antibody) assessment
- Record changes in concomitant medication/treatment – if any
- AE assessment
- Randomization
- Administer study medication in study eye only (if antimicrobial therapy taken as prescribed).

Day 1 (Postdose)

- Vital signs assessment
- IOP measurement for study eye only at 60 min (\pm 30 min) post injection
- Ophthalmoscopic examination in study eye only.
- Observe for at least 60 min (\pm 30 min) postdose (post injection)
- AE assessment

Note: * notes of screening visit to be followed.

6.3.1.2.2 Day 2 to 9

The Day 2 -9 visit can be on any day from Day 2 to Day 9.

- Vital signs assessment
- IOP measurement
- Ophthalmoscopic examination
- Slit lamp examination
- AE assessment
- Inquire if antimicrobial therapy is taken as prescribed
- Record changes in concomitant medication/treatment

6.3.1.2.3 Visit Days (\pm 2 days): Day 31, 61, 91, 121, 151, 181, 211, 241, 271, and 301

Pre dose

- Vital signs assessment
- Urine pregnancy test in females of childbearing potential
- Perform physical and systemic examination
- Record ECG (only at Day 181)
- Perform clinical laboratory assessment (hematology, biochemistry and urinalysis) at Day 91, Day 181, and Day 271.
- Ophthalmic Examinations: Unless otherwise stated these will be done for both the eyes

- Refraction assessment
- BCVA using ETDRS*
- Ophthalmoscopic examination
- Slit lamp examination
- IOP measurement (Obtained pretreatment for both eyes)
- Interviewer administered NEI-VFQ-25 at Day 91 and Day 181.
- Immunogenicity (anti-drug antibody) assessment at Day 31, Day 91, Day 181, and Day 271.
- Record changes in concomitant medication/treatment
- AE assessment

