9.1.1.1 Adverse Event

An AE is defined as any untoward medical occurrence in a patient or clinical investigation patient administered a pharmaceutical product and which does not necessarily have a causal relationship with this treatment. An AE can therefore, be any unfavorable and unintended sign, symptom, or disease (including intercurrent illness), deterioration of a pre-existing illness, accident, any suspected drug reaction, or a clinically relevant change of laboratory values temporally associated with the use of a medicinal (investigational) product, whether or not related to the medicinal (investigational) product and/or study treatment.

A treatment-emergent AE (TEAE) will be defined as an AE that begins or worsens in severity after at least one dose of study drug has been administered.

See Section 9.7 below for the instances where a pregnancy should be reported as an AE.

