10 ASSESSMENT OF IMMUNOGENICITY

10.1 Anti-Drug Antibodies

Immunogenicity will be assessed in patients on Day 1 (pre-dose) and thereafter as per Table 1. Samples for immunogenicity will be collected prior to dosing. An appropriate and validated method will be used for assessment of anti-drug antibodies.

Note: A tiered approach will be followed for assessing antibody formation in response to IP administration. All samples will be screened for occurrence of binding antibodies. Samples that test positive will be subjected to a confirmatory assay. Samples that are positive on confirmatory assay will further be tested for assessing the titer and neutralizing potential.

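### The patient-level ADA rule, read literally, counts a positive pre-dose Day 1 sample, so antibodies that predate treatment can label a patient ADA-positive

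*Combined protocol and SAP*

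**What the plan says.** Section 11.8.1.7 gives the patient-level rule: "if at least one sample tests positive in the validated method during this study, the patient is evaluated as a positive patient". It sets no post-dose restriction and no condition on baseline status. The same section compares incidence between arms on Day 1 and at the end of months 1, 3, 6, 9 and 12, plans a similar analysis for neutralizing antibodies, and leaves details to the SAP.

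Day 1 is a study sample. Note 20 to Table 1 reads "Blood samples for immunogenicity to be collected, before dosing study drug (predose) at Day 1", followed by the later visits, and the Day 1 pre-dose list in Section 6.3.1.2.1 includes "Immunogenicity (anti-drug antibody) assessment". Section 10.1 screens all samples and does not exempt Day 1.

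On purpose, Section 10.1 says "A tiered approach will be followed for assessing antibody formation in response to IP administration". Section 3.3 notes that with the reference product "both pre-treatment and post treatment incidences of antibodies have been reported". The endpoint in Section 5.2.3 is by visit and after baseline: "Proportion of patients with anti-drug antibodies at the end of 1, 3, 6, 9, and 12 months".

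**The concern.** The rule and its stated purpose do not match. Antibodies found before the first injection cannot be a response to the study product, but the rule as written counts them. For adverse events the protocol draws this line: Section 9.1.1.1 defines a treatment-emergent event as "an AE that begins or worsens in severity after at least one dose of study drug has been administered". The text reviewed has no counterpart for ADA. The Immunogenicity Analysis Set (Section 11.6.4) does not supply one, because it requires a valid post-baseline result but not a negative baseline.

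Comparative immunogenicity is a secondary objective (Section 4.2), and Section 3.3 treats it as a key part of a biosimilar programme. Randomization makes pre-existing positives equally likely in both arms. In a cumulative any-positive summary they add the same expected background to each arm. That pulls the ratio toward 1, in the direction of apparent similarity, and adds noise to the difference.

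**Working it through.** **No figure to reproduce.** The documents state no ADA rate, ADA sample size or ADA test. The only document inputs are the rule (Section 11.8.1.7), the Day 1 sample (Table 1, note 20) and 600 patients randomized 1:1, or 300 per arm (Section 11.1). Every rate below is an assumption.

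**Notation.** b is the proportion positive on Day 1, equal in both arms: 2% / 5% / 10%. t is the proportion of Day 1-negative patients who become positive after dosing.

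**Step 1: who carries the label.** Under the any-sample rule, P(labelled positive) = b + (1 − b)t. The share already positive on Day 1 is b / [b + (1 − b)t]. With t = 4% in both arms:

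| b | Labelled positive | Share already positive on Day 1 | Per 300 patients |
|---|---|---|---|
| 2% | 0.02 + 0.98 × 0.04 = 0.0592 | 34% | 6 of 17.8 |
| 5% | 0.05 + 0.95 × 0.04 = 0.0880 | 57% | 15 of 26.4 |
| 10% | 0.10 + 0.90 × 0.04 = 0.1360 | 74% | 30 of 40.8 |

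With t = 2% the shares are 51% / 73% / 85%; with t = 6% they are 25% / 47% / 65%. This step needs no assumption about how long antibodies persist.

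**Step 2: a cumulative between-arm summary of that label.** Take t = 2% v 6%, a true ratio of 3.0 and a true difference of 4.0 points.

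| b | Any-sample rates | Ratio | Difference (points) |
|---|---|---|---|
| 2% | 3.96% v 7.88% | 2.0 | 3.9 |
| 5% | 6.90% v 10.70% | 1.6 | 3.8 |
| 10% | 11.80% v 15.40% | 1.3 | 3.6 |

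The difference shrinks only by the factor (1 − b).

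**Step 3: precision of the difference.** The Wald 95% half-width is 1.96 × √{[p₁(1 − p₁) + p₂(1 − p₂)] / n}. With the any-sample rates and n = 300 it is 3.76 / 4.52 / 5.48 points. In Day 1-negative patients, with 2% v 6% and n = 300(1 − b) = 294 / 285 / 270, it is 3.15 / 3.20 / 3.29 points. At b = 5%, for example, the comparison is 3.8 ± 4.5 under the literal rule and 4.0 ± 3.2 in baseline-negative patients.

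**Step 4: the by-visit proportions, a separate question.** If a fraction p of pre-existing antibodies is still detectable at a visit, the rate there is bp + (1 − b)t. With p = 0 the ratio stays 3.0 for every b; with p = 0.5 it is 2.3 / 1.9 / 1.5. This comes from the by-visit endpoint not separating baseline positives. It would be the same if the patient-level sentence were deleted.

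**The case against.** **The rule feeds no stated test.** The endpoint and the stated comparisons are by visit, Day 1 is its own time point, and there is no margin or decision rule. This stands, and it limits the point to the patient-level label and any cumulative summary. A reader might infer that the sentence biases the Month 1 to 12 tests. The documents do not support that: those proportions are affected only if pre-existing antibodies persist, which is a different mechanism.

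**Details are deferred to the SAP.** No separate SAP is part of the text reviewed, and it may define treatment-emergent ADA. A reader might infer that the plan as a whole lacks the definition; that cannot be concluded. Even so, the protocol already states a rule. If the SAP differs, the two need aligning; if it is silent, the literal rule applies.

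**A post-dose reading is available.** Section 10.1's stated aim, the post-baseline endpoint and the analysis set all point that way. A reader might infer that the sponsor means to count Day 1 positives, but the text shows an ambiguity, not an intention.

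**The numbers are assumed and may be high.** This is true. Exclusion criterion 12 bars prior intravenous or intravitreal anti-VEGF treatment, which may keep Day 1 positives few. The risk difference hardly moves in any scenario. The illustration also leaves out boosted responses, so it does not measure the full benefit of the proposed definition.

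**Conclusion.** The concern holds in a limited form. As written, the patient-level rule admits a Day 1 positive, which is at odds with the testing aim in Section 10.1 and with the pre-treatment antibodies acknowledged in Section 3.3. The label may largely reflect antibodies that predate treatment, and a cumulative ratio built on it would understate a true difference between arms. The risk difference is nearly unchanged but less precise.

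These sizes rest on assumed rates, equal Day 1 prevalence in the two arms, and an induced rate that applies only to Day 1-negative patients. If Day 1 positivity is close to zero, the effect is negligible.

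A reader might also infer a threat to the biosimilarity conclusion. The documents do not support that: the primary equivalence test on BCVA does not use ADA status, and no immunogenicity criterion is set. Severity is minor to moderate.

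**What to change.** - Limit the patient-level rule in Section 11.8.1.7 to post-dose samples positive in the confirmatory assay.
- Define treatment-emergent ADA as induced (Day 1 negative, confirmed positive after dosing) or boosted (Day 1 positive with a pre-specified titre rise). Apply the same approach to neutralizing antibodies.
- Report Day 1-positive patients separately by arm, and state how a missing Day 1 result is handled.
- Alongside the planned by-visit summaries, give the between-arm difference in cumulative treatment-emergent ADA with a 95% confidence interval.
- If the SAP already contains this definition, align the protocol sentence with it.

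The cost is wording and programming, settled before unblinding. Day 1 samples are already collected, and Section 10.1 already plans the titres: "Samples that are positive on confirmatory assay will further be tested for assessing the titer and neutralizing potential". The downside is a slightly smaller denominator for the treatment-induced comparison: 294 / 285 / 270 instead of 300 per arm in the illustration. Against 66% power with 300 per arm and no pre-existing antibodies, an exact two-sided Fisher test at 5% of 2% v 6% would then have 65% / 63% / 60%.
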